250422. Analysis plan: Twin threat of OSA and hypertension on mortality and protective effect by positive airway pressure treatment. ClinicalTrials.gov Identifier: NCT06930989

250422 Gothenburg, Sweden

Analysis plan: Twin threat of OSA and hypertension on mortality and protective effect by positive airway pressure treatment.

ClinicalTrials.gov Identifier: NCT06930989

[name]

[contact]

[name]

Analysis plan: Twin threat of OSA and hypertension on mortality/CV-risk and protective effect by positive airway pressure treatment.

HYPOTHESIS

1. Patients with hypertension and obstructive sleep apnea (OSA) have increased risk of MACE (major cardiovascular events and death from these events; stroke, cardiovascular death, acute myocardial infarction, incident heart ischemia or heart failure) or premature death of any cause compared to HT alone or OSA alone and compared to healthy controls.
2. OSA patients compliant with PAP have reduced OSA related risk.

STUDY DESIGN

Discovery[1] (“Course of DISease in patients reported to the Swedish CPAP Oxygen and VEntilator RegistrY”) 2.0 is a large clinical cohort on patients with home mechanical ventilation, long-term oxygen treatment and/or CPAP treatment with data from the Swedish national register for patients on Long Term Oxygen Therapy and Home Mechanical Ventilation (Swedevox) and the Swedish Sleep Apnea Registry (SESAR). Data are cross referenced using Swedish personal IDs with data from multiple Swedish national registries including the National Patients diagnosis registry, National prescription registry, National Cause of Death Register, and SCBs registries on socioeconomic information. Data quality in the SWEDEVOX and SESAR registries have been validated for accuracy[2].

The following *inclusion criteria* will be applied:

- All adult patients that started PAP treatment during 2010-2021 in Swedevox with diagnosis of OSA with or without comorbid hypertension diagnosis within 5 years prior

initiation of CPAP therapy.

- Randomly selected individuals from the general population without a known OSA diagnosis but with and without arterial hypertension are selected for control groups.

Exclusion criteria for study participation are:

- Patients with manifest cardiovascular disease (stroke, ischemic heart disease, cardiac failure or atrial fibrillation at baseline).
- Patients with kidney failure at baseline.
- Patients with malignant cancer at baseline.
- Subjects with missing data on any of the main variables in the fitted models.

January 2010 is the start date for the non OSA groups. Follow-up time for the study will be until end of October 2022.

Hazard ratios from Cox proportional survival analyses for all-cause death and first MACE event (including CV death events) will be calculated controlling for anthropomorphic data (age, Body Mass Index (BMI), sex), comorbidities (hyperlipidemia, diabetes, depression and obstructive lung disease) medication (AHTs, statins and compliance of these drugs), and number of AHTs at baseline and socioeconomic factors (education level and income) and differences in age at first event between groups will be evaluated. Secondary analyses will investigate hazard ratios for all cause death and first MACE in OSA and HT+OSA groups, stratified by hourly usage per day of PAP to evaluate potential protective effect of PAP treatment on outcomes.

250422. Analysis plan: Twin threat of OSA and hypertension on mortality and protective effect by positive airway pressure treatment. ClinicalTrials.gov Identifier: NCT06930989

Hypertension at baseline is defined as having both hypertension diagnosis AND being prescribed at least one AHT drug. AHT drug is defined as intake of betablockers, diuretics, calcium channel blockers, Renin-Angiotensin-System blockers or centrally acting antihypertensives. Drug dispensation data will be used for assessment of patient compliance with drug treatment. Compliance with prescribed AHT and statins will be categorized as follows: At least 2 drug dispensations per year for $\frac{3}{4}$ of the study time with active prescription of that drug for each individual AHT group or statin required for high compliance. Total AHT compliance will require high compliance of all prescribed AHTs for more than $\frac{3}{4}$ of the individual study time, while patients only taking some of the prescribed AHTs will count as low combined compliance. The $\frac{3}{4}$ of study time criteria is used in order to avoid misclassifying change of AHT as poor compliance.

Ethical considerations

The study protocol was approved by the Ethics Committee at the Medical Faculty at Lund University and the Swedish Ethical Review Authority, Dnr. 2018/51, 2019/01420, 2020/02721, 2021/04984, 2022-00745-02, 2022-02012-02, 2022-05523-02, 2024-05277-02, and 2025-00712-02. According to Swedish law, patients entering a national quality registry like Swedevox are informed, can withdraw from registration at any time, but do not sign an informed consent.

Statistical analyses

Continuous data following a normal distribution will be reported as mean \pm standard deviation (SD), while data with a skewed distribution will be presented as median along with the interquartile range (IQR). Categorical data will be represented as frequencies and percentages. Categorical variables will be

analyzed with the chi-squared test, normally and non-normally distributed continuous variables will be analyzed with Student's t-test and the Wilcoxon rank-sum test respectively. ANOVA is used to compare variables between groups.

Medians and 95% CI are reported for follow-up time for the groups and total.

Mortality and MACE incidence will be visualized using Kaplan-Meier cumulative mortality/incidence estimate curves. Survival differences between groups will be analyzed using log-rank tests. Crude and adjusted Cox proportional survival analyses will be made. Covariates are selected using current literature, clinical experience and directed acyclic graphs. Hazard Ratio, Relative Risk, and CI are reported for COX analyses. Separate Cox proportional survival analyses will be made to investigate difference between the two OSA groups and to assess PAP protective effect and adherence in a similar manner.

Both all-cause death and MACE/CV related deaths will be reported separately for primary and secondary outcomes.

All estimates will be presented with 95% confidence intervals (CIs). Statistical significance is defined as a two-sided p-value < 0.05.

DATA MANAGEMENT

Definition of primary outcome

Hazard ratios for all groups MACE/death event risk. Mean age at MACE/death event for all groups.

Definition of secondary outcome

[figure not shown]
Modifying effect of PAP treatment analysis stratified by compliance/daily usage time per night on primary outcomes.

Definition of exposure

Hypertension diagnosis and or OSA for primary outcomes.

PAP treatment (Swedevox 2010-2023) for secondary outcomes.

DAG:

Lifestyle factors include smoking, food habits and physical activity, where we lack data. Will be indirectly controlled for thru inclusion of socioeconomic factors, anthropometrics, compliance of treatments and obstructive lung disease.

Analysis plan: The synergistic effect of OSA and hypertension on mortality can be attenuated by positive airway pressure treatment.

Variables and timing of variables to be obtained from database(s):

Below are the variables to be considered in the analysis listed.

All non-outcome variables for baseline inclusion as well as latest available at study end. For sleep data first available data will be considered baseline information.

Sleep data

AHI, ODI, ESS (Epworth sleepiness scale), mean saturation. Date of OSA diagnosis and PAP start.

Baseline or if missing; above mentioned data are possibly available from the CPAP start. For sleep data first available data will be considered baseline information.

Sleep follow-up data during treatment follow-up

PAP compliance (hrs/day) closest before MACE/death or end of study. Continuous and stratified compliance and considered to have the same compliance for rest of study duration.

ESS.

Medication

All **AHT before PAP start, last year before MACE/death or study end.** Patients picking up a drug at least twice during the last year are considered on that drug for a visit. *Dosing needed separately for each drug.*

Statins at baseline and end of study.

Number of medication pickup dates for each calendar year will be calculated and used for compliance estimations.

Diagnosis

All diagnoses before PAP start and end of study. MACE or new AF *at any time.* Reasons for death when applicable.

ICD codes of interest (both patient registries and/or swedevox):

Diabetes (E10-E14), Hyperlipidemia E78, COPD J44, Kidney failure (N17-N19), Depression F32 and 33, Hypertension (I10-I15), OSA G47.3, ischemic heart disease (I20-25), AF I48, Cardiac failure I50, Stroke I61-66. Malignant cancer C00-C97. Ischemic heart disease or infarction, Atrial fibrillation, Cardiac failure or Stroke *Baseline and first new diagnosis for MACE.*

All else *baseline and study end.*

Socioeconomic data

Baseline and study end. European socioeconomic classification (ESeC/YSEG in SCB), Education level, Income quartiles.

Smoking

Indirectly assessed through “Obstructive lung disease” (diagnosis captured from medication use), socioeconomic variables, BMI and compliance with primary preventive treatments.

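### OSA patients who start PAP while also on long-term oxygen or home mechanical ventilation are neither excluded nor adjusted for, so all-cause death against the population controls may be inflated

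*SAP*

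**What the plan says.** Under STUDY DESIGN the SAP describes its source as a "large clinical cohort on patients with home mechanical ventilation, long-term oxygen treatment and/or CPAP treatment". The and/or means that one person can hold more than one of these treatments.

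The OSA groups are "All adult patients that started PAP treatment during 2010-2021 in Swedevox with diagnosis of OSA", with or without hypertension. The look-back for hypertension ends at "initiation of CPAP therapy". The SAP does not define PAP as CPAP only. The controls are "Randomly selected individuals from the general population without a known OSA diagnosis", with and without hypertension.

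The baseline exclusions are:
- "Patients with manifest cardiovascular disease (stroke, ischemic heart disease, cardiac failure or atrial fibrillation at baseline"
- renal failure, or a malignancy, already present at that time
- missing data on a main model variable.

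The adjustment lists (STUDY DESIGN and Main Analysis) contain BMI and obstructive lung disease, but no term for oxygen, ventilation or respiratory failure. Under Diagnosis, COPD is the only lung disease given a code. Mean saturation is collected under Sleep data but is not in the main model list. The main analysis compares every group with healthy controls on all-cause death and on MACE.

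**The concern.** By removing cardiac, renal and malignant disease at baseline, the plan tries to separate the risk of OSA and hypertension from that of other serious illness. Chronic respiratory failure treated at home is left in, although the source register records that treatment.

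The omission is not symmetric. The OSA groups come from a register of respiratory treatment and the controls from the general population. Deaths from respiratory failure among OSA patients who also use oxygen or a ventilator could therefore be credited to OSA. That would favour the first hypothesis, which predicts higher risk in patients with both conditions. A large cohort does not shrink this bias.

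**Working it through.** **Text check.** Oxygen and ventilator treatment are named in the cohort description only. They do not appear in the inclusion criteria, exclusions, covariates, diagnosis codes or secondary analyses.

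**Size.** The SAP states no prevalence, event count or hazard ratio, so there is no figure of its own to reproduce. What follows is an illustration on assumed inputs.

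From the SAP:
- PAP start 2010–2021, taken as uniform entry over 12 years.
- Follow-up to the end of October 2022, 12.83 years after January 2010. Follow-up T is then uniform from 0.83 to 12.83 years.

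Assumed:
- Mortality λ = 0.012 a year in controls and in the other OSA patients, so the true ratio is 1.0.
- A share p of OSA patients on oxygen or a ventilator at entry: 0.5%, 1% or 2%.
- Mortality k times λ in that share: 3, 5, 10 or 20.
- No controls on either treatment, and no covariate adjustment.

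The probability of dying during follow-up at hazard h is

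D(h) = 1 − [exp(−0.83h) − exp(−12.83h)] / (12h),

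and the mean person-years are D(h)/h. The apparent rate ratio is

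RR = [(1−p)·D(λ) + p·D(kλ)] / [(1−p)·D(λ)/λ + p·D(kλ)/(kλ)] ÷ λ.

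Example with p = 1% and k = 10:
- D(0.012) = 0.07789, with 6.491 person-years. D(0.12) = 0.5203, with 4.336 person-years.
- Deaths per patient: 0.99 × 0.07789 + 0.01 × 0.5203 = 0.08232.
- Person-years per patient: 0.99 × 6.491 + 0.01 × 4.336 = 6.470.
- RR = 0.08232 / 6.470 / 0.012 = 1.06.

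| Share p | k = 3 | k = 5 | k = 10 | k = 20 |
|---|---|---|---|---|
| 0.5% | 1.009 | 1.017 | 1.030 | 1.045 |
| 1% | 1.018 | 1.033 | 1.060 | 1.090 |
| 2% | 1.036 | 1.066 | 1.121 | 1.180 |

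**Cross-check.** A simpler frame, with 6 years of follow-up for everyone and 1% yearly mortality, gives 1.036 (p = 1%, k = 5), 1.07 (1%, 10) and 1.14 (2%, 10), close to the table. In the same frame a share of 5% would give 1.18 (k = 5) or 1.35 (k = 10), so the answer depends on the unknown share.

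**Which comparisons are exposed.**
- OSA or OSA+HT against either control group, all-cause death: exposed, because only one side is drawn from the treatment register.
- The same comparisons on MACE: probably less affected, because respiratory deaths are not MACE events.
- OSA+HT against OSA-only: both sides come from the same register, so the excess largely cancels unless the share differs by hypertension status.

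**The case against.** The strongest reply is that the affected group is narrow. Entry needs both an OSA diagnosis and a PAP start, and the CPAP wording at the end of the criterion suggests that CPAP starters are meant. A reader might infer from the cohort description that patients on oxygen or a ventilator alone, without OSA, are in the OSA groups. The inclusion rule does not support that. This limit stands: only concurrent users matter, or OSA patients whose PAP was a ventilator mode if PAP is meant that broadly. The CPAP phrase, however, only dates the look-back and excludes nobody who also has oxygen or a ventilator.

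Second, existing features absorb part of the risk. The cardiac, renal and cancer exclusions remove conditions that can accompany chronic respiratory failure, and BMI and obstructive lung disease are adjusted for. This also stands in part. But obstructive lung disease is identified from medication use (Smoking section), carries no grade of severity, and misses non-obstructive reasons for ventilation.

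Third, a plan need not exclude every serious comorbidity; diabetes and lung disease are kept and adjusted for. That is fair, and nothing here contradicts the plan's own text. The difference is that this condition is neither excluded nor adjusted for.

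The protocol is not at hand, but the SAP sets out its own eligibility and covariate lists, and the gap is in those.

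**Conclusion.** The gap is real but narrow. Concurrent users of long-term oxygen or home ventilation can enter the OSA groups with nothing in the analysis to account for them, so all-cause death against the control groups may be inflated.

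Under the stated assumptions, a true ratio of 1.0 rises to at most 1.09 at a share of 1% or less and to at most 1.18 at 2%, before adjustment. With 3 to 5 times the mortality, the range across all three shares is about 1.01 to 1.07. Adjustment for BMI and obstructive lung disease should reduce these figures by an unknown amount.

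Two stronger readings are not supported. A reader might infer that mortality in the OSA groups is certainly inflated; without the number of such patients, the documents show only that it could be. A reader might also infer that the analysis by PAP hours is distorted. Hours of use in these patients may reflect their underlying disease, but the documents support neither a direction nor a size.

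**What to change.** State whether PAP means CPAP only, and add one exclusion that applies to every group:

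> Patients registered in Swedevox for long-term oxygen therapy or home mechanical ventilation at or before PAP start (OSA groups) or January 2010 (controls).

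Report the number removed from each group, which also settles how much the point matters.

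The cost is one line that uses register fields in the same cohort. A few patients are lost, and the results no longer apply to OSA with concurrent oxygen or ventilator treatment.

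### The main Cox models adjust for drug compliance scored over follow-up that ends at the event, so the compliance coefficient can be false and can shift the hypertension hazard ratios

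*SAP*

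**What the plan says.** Under Study Design, high compliance with one AHT group or a statin means at least two dispensations a year for three quarters "of the study time with active prescription of that drug for each individual AHT group or statin required for high compliance". Total AHT compliance requires high compliance with every prescribed AHT for more than three quarters "of the individual study time, while patients only taking some of the prescribed AHTs will count as low combined compliance". These are two different denominators. The stated purpose is that the three quarters "of study time criteria is used in order to avoid misclassifying change of AHT as poor compliance". The Medication section adds: "Number of medication pickup dates for each calendar year will be calculated and used for compliance estimations". No rule for part-years is given.

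The Cox models are to adjust for "medication (AHTs, statins and compliance of these drugs), and number of AHTs at baseline". The variable list under Main Analysis again includes AHT compliance, statin use and statin compliance. Every group is compared with healthy controls, and follow-up stops at the first event. No pre-index window, lag, landmark or time-updating is specified for drug compliance, and no code is given for people without a prescription.

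Two further statements matter. "Hypertension at baseline is defined as having both hypertension diagnosis AND being prescribed at least one AHT drug". And time zero differs by group: "January 2010 is the start date for the non OSA groups", whereas the OSA groups are "All adult patients that started PAP treatment during 2010-2021 in Swedevox".

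**The concern.** A Cox covariate treated as fixed should be known at the start of follow-up. This one is known only when the person's follow-up is over. I read individual study time as time at risk, so the outcome itself sets the length of the scoring window. Two people with the same refill habits can get different labels because one had an early event, and the model then reports a compliance effect that need not exist.

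The error need not stay in the compliance coefficient. The label applies to all HT persons and to few in the reference groups, so the HT term and the label are tied together. A false coefficient can move the HT hazard ratios, which are the primary outcome. The Main Analysis option to leave out variables without effect gives no protection, because a false effect would keep the term in.

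**Working it through.** The SAP gives no sample size, event count or effect size, so there is no figure of its own to reproduce.

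**1. Same behaviour, different label.** From the SAP: two dispensations a year, the 3/4 threshold, counts per calendar year. Assumed: on-time 90-day refills starting on the index date. Three readings of a part-year are compared: each calendar year counts equally; years are weighted by days but still need two pickups; or the required pickups are prorated (2 × year fraction).

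| Entry to event | Equal weight | Time-weighted | Prorated |
|---|---|---|---|
| 1 Jan 2010 to 1 Mar 2012 | 2/3 = 67%, low | 730/790 days = 92%, high | 92%, high |
| 1 Jan 2010 to 1 Mar 2014 | 4/5 = 80%, high | 1461/1520 = 96%, high | 96%, high |
| 1 Nov 2012 to 15 Feb 2018 | 5/7 = 71%, low | 1826/1932 = 95%, high | 100%, high |
| 1 Nov 2012 to 1 Mar 2013 | 0/2, low | 0/120 = 0%, low | 100%, high |

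In the last row there is one pickup in 2012 (1 November) and one in 2013 (30 January). Neither year reaches two, but both exceed the prorated need (2 × 61/366 = 0.33 and 2 × 59/365 = 0.32). Entry late in a year is possible only in the OSA groups.

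**2. Complete years only.** Suppose each year independently reaches two pickups with probability p. After k years, P(high) = P(Bin(k, p) ≥ ⌈0.75k⌉). For p = 0.85 and k = 1, 2, 3, 4, 12 this is 0.85, 0.72, 0.61, 0.89, 0.91. For example, k = 4 gives 0.85⁴ + 4 × 0.85³ × 0.15 = 0.89. For p = 0.60 it is 0.60, 0.36, 0.22, 0.48, 0.23. The label depends on follow-up length, and not in one direction.

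**3. Effect in a Cox model.** Simulated data with compliance having no effect and a true HT hazard ratio of 1.5. From the SAP: controls from January 2010, OSA entry 2010-2021, end October 2022. Assumed: events 2%/year without HT and 3%/year with HT; 70% refill every 90 days and 30% every 300 days; one to three AHTs per HT person; number of AHTs in the model. With the active-prescription denominator, the false low-v-high hazard ratio was:

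| Year rule | HT-only v healthy | OSA+HT v OSA-only |
|---|---|---|
| Equal weight | 1.29 | 2.16 |
| Time-weighted | 1.13 | 1.46 |
| Prorated | 1.01 | 1.11 |

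**4. Transfer to the HT hazard ratio** (crude 1.44-1.52). With equally weighted years, no AHT use in the reference group and no stopping of drugs, HT-only v healthy was 1.31 with non-users coded not low and 1.80 with non-users coded low. OSA+HT v OSA-only was 1.10 and 2.47; OSA+HT v healthy was 1.09 and 2.46. With no users in the reference group, the two codings differ exactly by the false coefficient (2.47/1.10 = 2.25). With 15% use in the reference group, and stopping of 0 or 5%/year per drug, the ranges over both codings narrow to 1.36-1.70, 1.21-1.94 and 1.30-1.82. Time-weighted years gave 1.40-1.69 for HT-only v healthy (no use in the reference group). Prorated part-years gave 1.41-1.61 overall.

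**5. What moves little.** OSA+HT v HT-only was 0.96-1.00 (truth 1.0), because both groups carry the label. With statin use in the model and equally weighted years, the HT hazard ratio v healthy was 1.49-1.52, but the false statin-compliance hazard ratio was 1.27-1.92.

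**6. Sensitivity to the refill model.** With random (Poisson) pickups varying between persons, and part-years prorated, the high-v-low hazard ratio ran from 0.75 to 1.09 and the HT hazard ratio from 1.32 to 1.86. With regular refills and a pickup on the index date, prorating gave a low-v-high value of 0.82-0.93, the opposite direction to the table in step 3.

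**The case against.** **The rule is a share of time.** Study Design asks for a rate over a share of study time and does not say that a two-month part-year counts as a full one. A reader might infer from the calendar-year counts that the 1 March 2012 patient is certainly classed low. The SAP does not say so, and as a share of time that patient is at 92%. This stands, and it removes the largest figures as a prediction. It does not remove the dependence on follow-up: the fourth row of the first table is low under time-weighting too.

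**Antihypertensives are listed separately from their number.** The adjustment sentence can be read as including an any-AHT term. With 15% use in the reference group, that term held the HT hazard ratio at 1.44-1.52. Such users can exist, because HT needs a diagnosis as well as a drug. This stands in part: Main Analysis does not repeat the item, the protection needs users in the reference group, and the compliance hazard ratio remained false at 1.31-2.18.

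**Non-users coded low.** The upper HT values need people without a prescription to be classed low, which is strained when the SAP speaks of compliance with prescribed drugs. This stands.

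**Stopped drugs.** A reader might infer from the individual-study-time denominator that longer survivors become low because they have had time to stop a drug. That needs a stopped drug to go on counting as prescribed, which the SAP does not state and which defeats its own aim. It supports only the request for one denominator.

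**Other safeguards.** A crude Cox model is planned and is untouched, but it has no confounder adjustment and cannot replace the adjusted one. Compliance is also a deliberate proxy for unmeasured lifestyle. That is a cost of removing it, and a pre-index version can serve the same purpose.

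**Conclusion.** The point holds as a fault in how the covariate is defined. The SAP scores AHT and statin compliance over follow-up that ends at the outcome and enters the result in the main models as a fixed covariate. The coefficient can be false, and HT v healthy, OSA+HT v healthy and OSA+HT v OSA-only can shift with it.

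The SAP supports no specific size or direction. Under assumed regular refills the false effect is clear with equally weighted calendar years, smaller with time-weighted years, and near zero to small with prorated part-years under the active-prescription denominator. Another refill pattern changes these values. All simulated figures illustrate the mechanism and do not forecast the result. A reader might infer that the primary hazard ratios are bound to be badly biased; the document does not support that, because the wide ranges rest on part-year and coding choices it does not make. OSA+HT v HT-only is little affected, and nothing is claimed for the PAP analyses. This should be fixed before analysis, but it does not by itself invalidate the plan.

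**What to change.** 1. In the main adjusted model, keep baseline number of AHTs and baseline statin use. Either omit compliance, or define it only from dispensations in a fixed window (for example 12 months) before the index date: January 2010 for controls, PAP start for the OSA groups. Code prescribed and low as 1 and everyone else, including people without a prescription, as 0. State that the HT hazard ratio then refers to compliant HT patients.
2. Report on-treatment compliance only as a secondary analysis within drug users, lagged and time-updated or from a landmark, with part-years prorated.
3. Replace the two denominators with one.

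In the same simulations, the HT hazard ratio was 1.44-1.54 without the term. It was also 1.44-1.54 with a 12-month pre-index label, whose own hazard ratio was 0.98-1.01. Within the HT groups the compliance hazard ratio was 0.99-1.02 from a 12-month landmark and 0.99-1.03 lagged and time-updated.

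The cost is SAP wording and a recode of dispensation data. Omitting compliance loses part of the lifestyle control described with the DAG. The pre-index version needs 2009 dispensations for controls, which the SAP does not say are held, and newly started drugs have a short history. A landmark drops early events.

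### Codes for hypertensive heart and renal failure (I11.0, I12.0, I13.0-I13.2) count as hypertension but not as cardiac or kidney failure, so the baseline exclusions and the heart-failure part of MACE misclassify some patients, mainly hypertensive ones

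*SAP*

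**What the plan says.** The exclusion criteria under Study Design remove "Patients with manifest cardiovascular disease (stroke, ischemic heart disease, cardiac failure or atrial fibrillation at baseline" and, separately, "Patients with kidney failure at baseline". The Hypothesis section defines MACE as "stroke, cardiovascular death, acute myocardial infarction, incident heart ischemia or heart failure", so heart failure is a component and renal failure is not.

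The codes are given under Diagnosis: "Kidney failure (N17-N19), Depression F32 and 33, Hypertension (I10-I15), OSA G47.3, ischemic heart disease (I20-25), AF I48, Cardiac failure I50, Stroke I61-66". The same section uses the cardiac codes both for baseline status and for the endpoint: "Cardiac failure or Stroke *Baseline and first new diagnosis for MACE".

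Study Design also requires a hypertension diagnosis together with at least one antihypertensive drug before a person counts as hypertensive at baseline. The Death registry section lists I20-I25, I46, I48, I50 and I61-I66 for CV death. Nothing in the SAP takes the failure subcodes out of I10-I15 or adds them to the failure definitions.

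**The concern.** The SAP uses ICD-10, and in that classification some codes between I10 and I15 record hypertension and organ failure together. I11.0 and I13.0 carry heart failure, I12.0 and I13.1 carry renal failure, and I13.2 carries both. The plan reads all of them as hypertension and none as failure.

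Two errors follow when the plan is applied as written.

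- **Gap (a), entry.** A treated patient whose failure is recorded only under one of these codes should be excluded. Instead, the same code supplies the diagnosis half of the hypertension definition, and the patient enters HT-only or OSA+HT. If I50 is first recorded during follow-up, pre-existing heart failure is also counted as a new MACE.
- **Gap (b), endpoint.** Incident heart failure recorded only as I11.0, I13.0 or I13.2 is not a MACE, although heart failure is a named component.

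Both errors are tied to the exposure under study. The main analysis compares every group with healthy controls, and a secondary analysis compares OSA+HT with OSA-only. Both comparators are defined by the absence of hypertension at baseline, so the error does not fall equally on the two sides. Because it is systematic, a large cohort will not average it out. The covariates listed under Main Analysis include neither heart failure nor kidney failure, since the plan relies on having excluded both.

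**Working it through.** The SAP states no sample size, event count or code frequency, so there is no figure of its own to reproduce. The check has two parts: membership of the codes in the plan's own lists, and a range on assumed inputs.

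**1. Code membership**

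| Code block | Hypertension (I10-I15) | Baseline exclusions (I20-I25, I48, I50, I61-I66, N17-N19) | Cardiovascular diagnoses used for MACE | CV-death list |
|---|---|---|---|---|
| I11 | yes | no | no | no |
| I12 | yes | no | no | no |
| I13 | yes | no | no | no |

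The I12 row matters only for the exclusion, because renal failure is not a MACE component.

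**2. Gap (a): prevalent failure admitted.** Let q be the share of a hypertensive group that has admitted failure and r their hazard relative to the rest of the group. The crude multiplier on the group's rate, and so approximately on its hazard ratio against an unaffected comparator, is 1 + q(r - 1). Both q and r are assumptions.

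| q | r = 3 | r = 5 | r = 8 |
|---|---|---|---|
| 0.25% | 1.005 | 1.010 | 1.0175 |
| 0.5% | 1.010 | 1.020 | 1.035 |
| 1% | 1.020 | 1.040 | 1.070 |
| 2% | 1.040 | 1.080 | 1.140 |

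With q = 3% and r = 5 the multiplier is 1 + 0.03 × 4 = 1.12.

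**3. Gap (b): incident heart failure not counted.** Let f be the share of a hypertensive group's first MACE that carries only the omitted codes and is never replaced by a later qualifying record. The observed hazard ratio is then about HR × (1 - f). For a true HR of 1.50:

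| f | observed HR |
|---|---|
| 1% | 1.485 |
| 2% | 1.470 |
| 5% | 1.425 |
| 10% | 1.350 |

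One way to build f is as the heart-failure share of first MACE (assumed 20-30%) times the share of it coded only under hypertension (assumed 10-30%). This gives 0.2 × 0.1 = 2% to 0.3 × 0.3 = 9%, or an observed HR of 1.47 to 1.365. If the comparator also loses a share f0, the factor is (1 - f)/(1 - f0), which is closer to 1. For example, f = 5% and f0 = 1% give 1.50 × 0.95/0.99 = 1.44.

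**4. Both gaps together, for MACE.** Taking (a) at 1.02 to 1.12 and (b) at 0.98 to 0.91, the product runs from 1.02 × 0.91 = 0.93 to 1.12 × 0.98 = 1.10. The range spans 1, so the net direction is not determined.

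**5. All-cause death.** Every death counts whatever its code, so gap (b) does not apply. Gap (a) acts alone, and upward.

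**6. OSA+HT against HT-only.** Both groups admit the same codes. If q and r are equal in the two groups, the multipliers cancel; if they differ, a remainder stays.

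**The case against.** The strongest reply is that everything depends on coding habit. The Diagnosis section draws on more than one source and on all diagnoses before PAP start, so a single I50 or N17-N19 record is enough to exclude. Prior ischaemic heart disease, atrial fibrillation or stroke excludes as well. Only patients with no such record are affected, and the SAP does not say how many there are. At the low end of the ranges the effect is negligible: 1.005 for gap (a), and 1.485 instead of 1.50 for gap (b). This stands, and it limits the size that can be claimed.

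Two technical objections also stand in part. First, a missed I11.0 event is often only delayed: a later I50, ischaemic, stroke or listed CV-death record still counts as MACE, so the values of f built from coding shares are upper figures for their inputs. Second, the multiplier for gap (a) is crude. The adjusted model includes the number of antihypertensives, compliance with them, and diabetes, and these could absorb part of the excess.

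A reader might infer three stronger things that the SAP does not support.

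- *New hypertensive renal failure is a missed MACE.* It is not, because the Hypothesis section does not list renal failure as a component. I12.0 and I13.1 matter only for the kidney exclusion.
- *Events are lost only in the hypertensive groups.* Groups are fixed by baseline status. OSA-only patients and healthy controls can develop hypertension and then heart failure coded I11.0, so the loss is concentrated in the hypertensive groups but not confined to them. For entry, the code alone does not make someone hypertensive either, since a drug is also required.
- *The error is known to favour the study's hypothesis for MACE.* The two gaps run in opposite directions and the net sign is open.

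None of this closes the gap between the stated exclusions and endpoint and the codes that implement them.

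**Conclusion.** The point holds as a code-list error tied to the exposure. Followed as written, the SAP admits some prevalent heart and renal failure that it says it excludes, and misses or delays some incident heart failure that it says it counts.

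The size is unknown. On assumed inputs each gap shifts the hazard ratio by between under 1% and roughly 10%, with gap (a) reaching 12-14% at the most extreme combinations. For MACE the net direction is undetermined. For all-cause death only gap (a) acts, raising the hazard ratios of the hypertensive groups against healthy controls and of OSA+HT against OSA-only. The OSA+HT versus HT-only contrast may partly cancel the error.

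The conclusion rests on the ICD-10 meaning of the subcodes and on some patients carrying them without I50 or N17-N19. The quantities q, r and f are illustrations, not estimates from the documents.

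**What to change.** - Define cardiac failure as I50, I11.0, I13.0 and I13.2, for both the baseline exclusion and the MACE component.
- Add I11.0, I13.0 and I13.2 to the CV-death list under Death registry. Otherwise the same code would count as a non-fatal MACE but not as a CV death within one composite.
- Define kidney failure as N17-N19, I12.0, I13.1 and I13.2, for the baseline exclusion. MACE does not change on this account.
- Keep the remaining I10-I15 codes as the hypertension exposure.
- Apply the lists identically in all four groups, and report how many people and events are reclassified. That count replaces the assumed ranges above.

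If the omission is deliberate, the SAP should say why and add a sensitivity analysis with the extended lists.

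The cost is an edit to three code lists and a re-run on registry data already extracted. It needs four-character codes, a level at which the SAP already specifies OSA (G47.3). The downside is that a few more hypertensive patients are excluded.
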